### **Study procedures:**

There will be a total of nine study visits over a period of 12 months, including the screening visit, four visits for monitoring adverse effects and compliance, and four visits for measuring study outcomes (two at Baseline and two at 12 months). Table 3 below outlines all study visits.

Screening visit: Screening for eligibility will include a brief cognitive screen with the Montreal Cognitive Assessment (MoCA). Detailed medical and psychiatric history, current medications, and medications used over

past 6 months will be reviewed. Potential participants will be administered the Structured Clinical Interview for DSM-IV--Patient Edition (SCID-IV) to diagnose exclusionary psychiatric disorders.

Table 3. Detailed Schedule of Study Visits

	Screen Visit	Baseline Visits		Safety Visits				12 mo Outcome	
		1 st	2 nd	6 wk	3 mo	6 mo	9 mo	1 st	2 nd
Demographics	X								
Medical/psychiatric/military history	X								
Physical/neurological examination	X							X	
CBC, Chem 7, TSH, B12, folate, albumin, routine urinalysis	X								
fasting lipid panel (HDL, LDL, triglycerides)	X	X						X	
Plasma homocysteine & C-reactive protein (CRP)		X						X	
LFTs, bilirubin, CPK, HbA1c	X			X	X	X	X	X	
Urine pregnancy test	X	X	X	X	X	X	X	X	X
APOE genotype	X								
LP – CSF biomarkers		X						X	
SCID-IV	X								
CAPS, SWLS			X						X
PCL-M, PHQ-9, AUDIT-C			X	X	X	X	X		X
MoCA	X		X	X	X	X	X	X	
Neuropsychological test battery			X						X
Vital signs	X	X	X	X	X	X	X	X	X
Review of concurrent medications	X	X		X	X	X	X	X	
Assess adverse events			X	X	X	X	X	X	X
Pill count for med compliance				X	X	X	X	X	
Dispense study medications			X	X	X	X	X		

A complete physical and neurological examination will be performed. Screening laboratory tests will be obtained, including complete blood count (CBC), chemistry panel, thyroid stimulating hormone (TSH), vitamin B12, folate, SGOT, SGPT, SGGT, bilirubin, alkaline phosphatase, CPK, albumin, and fasting lipid panel (total cholesterol, HDL, LDL, and triglycerides), urinalysis, and (in female subjects of childbearing potential) a urine pregnancy test. Blood samples will also be collected for apolipoprotein E (APOE) genotyping (described below). A urine sample will be obtained for routine urinalysis and (in female subjects of childbearing potential) a urine pregnancy test.

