To monitor for emergence or worsening of comorbid depression, the PHQ-9, a self-report measure of depression will be administered at all visits. The PHQ-9 score can range from 0 to 27. Scores of 5, 10, 15 and 20 represent thresholds demarcating the lower limits of mild, moderate, moderately severe and severe depression, respectively. If the PHQ-9 score is increased by 10 (i.e., an increase of two severity categories) compared to baseline, the subject will be terminated from the study. To monitor alcohol use and symptoms of comorbid PTSD, we will administer the AUDIT-C and the PCL-M at all visits.

If at any time during the study, a participant complains of symptoms which may indicate a potential adverse event, additional safety visit(s) as necessary will be performed. Procedures to be performed at additional visits will depend on the symptoms the participant is experiencing. If the participant meets any criterion for study removal (as described below), an early discontinuation visit will be performed.

**Early treatment discontinuation procedures:** The primary reasons for treatment discontinuation anticipated during the study are adverse effects, protocol violation, noncompliance, and withdrawal of consent. We will make every reasonable effort to keep each subject in the study. Every effort will be made to schedule a discontinuation visit as soon as possible following discontinuation of study medication to allow collection of outcome and safety measures.

**Criteria for termination from study:** Subjects will be removed from the study if they: 1) develop a significant adverse medication reaction, including psychiatric adverse effects; 2) exhibit >1 standard deviation decline on more than one component of the neuropsychological test battery; 3) develop a significant elevation in serum transaminases (i.e., > 3 X upper limit of normal for SGOT and/or SGPT) or CPK (i.e., > 10 X upper limit of normal); 4) have a positive urine pregnancy test; or 5) meet NCEP/ATP-III criteria for initiation of lipid-lowering therapy at the 3- or 6-month safety visits.

**Compliance with study medications:** Subjects will be given a 6-week supply of medication at Baseline and at the 6-week visit, and subjects will be given 3-month supplies of medication at the 3-, 6- and 9-month

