### **Statistical analysis.**

**Primary analysis plan:** All CSF biomarkers, neuropsychological test scores, behavioral assessments, and functional and quality of life measures are continuous variables. Gender, APOE genotype, and number of mTBIs ( $\geq 5$  or  $< 5$ ) are categorical. Analysis of covariance (ANCOVA) will be used to assess the change from the baseline in all biomarkers as well as neuropsychological test scores. All outcomes are continuous variables. The distribution of model residuals will be assessed and outcome variables may be transformed to conform to assumptions of the statistical tests (e.g., for non-normality). The response variables will be biomarker concentrations at the end of the study (12-month visit), and predictor variables will include biomarker concentrations at the beginning of the study (baseline visit), treatment arm assignment (simvastatin vs. placebo), as well as the variables that were used for stratification of treatment assignment (i.e., gender and number of blast exposures). To examine effects of statin treatment on memory and cognition, the response variables will be test scores at the end of the study (12-month visit). The predictor variables will include test scores at the beginning of the study (baseline visit), treatment arm assignment (simvastatin vs. placebo), as well as the variables that were used for stratification of treatment assignment (i.e., gender and number of blast exposures). Significance of treatment arm effect will be adjusted for multiple tests (i.e., the four primary endpoints) using the method of Holm (1979).

The primary analysis will include all subjects who were randomized and completed the study. A secondary analysis will use a linear mixed-effects model to include all subjects who were randomized and had a baseline visit, including subjects with just a baseline visit as well as subjects with a baseline visit and an early termination visit. Baseline differences, if any, between study completers and non-completers will be summarized.

**Secondary analysis plan:** In addition to the above primary analysis, secondary analyses will include the following:

- Correlation analyses to assess relationships among CSF biomarkers and how they change over time relative to each other.
- Exploring what other covariates (such as serum cholesterol levels) may be important in predicting changes from baseline in CSF AD biomarkers

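### The primary ANCOVA uses completers only, and most removal rules leave no planned month-12 outcome: CSF bias is probably small, but cognitive harm that persists in a subset would be understated

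*Combined protocol and SAP*

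**What the plan says.** Population and model, under Primary analysis plan:

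- "Analysis of covariance (ANCOVA) will be used to assess the change from the baseline in all biomarkers as well as neuropsychological test scores". The response is the month-12 value, with baseline, arm and stratification variables as predictors. Holm adjustment covers the four primary CSF endpoints.
- On the population for this analysis: "The primary analysis will include all subjects who were randomized and completed the study".
- The wider population is left to a supporting model: "A secondary analysis will use a linear mixed-effects model to include all subjects who were randomized and had a baseline visit". This includes subjects with baseline only and "subjects with a baseline visit and an early termination visit". The plan does not say whether an early-termination value enters as the follow-up value or at its own time.

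Removal, under Criteria for termination from study: the five criteria are worded as removal from the study. They include significant adverse reactions, transaminase or CPK elevation and pregnancy, and also apply to subjects who "exhibit >1 standard deviation decline on more than one component of the neuropsychological test battery" or who "meet NCEP/ATP-III criteria for initiation of lipid-lowering therapy at the 3- or 6-month safety visits". The cognitive threshold varies: two measures under Monitoring safety of participants, more than one component in the termination criteria, any single test under Protection Against Risk.

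After removal: every effort is made to "schedule a discontinuation visit as soon as possible following discontinuation of study medication to allow collection of outcome and safety measures". Laboratory stops are followed until values normalise. The Data Safety and Monitoring Plan allows re-evaluation for continuing after a psychiatric event. Table 3 places the lumbar puncture and the full battery only at baseline and month 12.

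**The concern.** Completers are selected after randomisation, so randomisation alone no longer makes the arms comparable. The selection can differ by arm. The protocol names raised transaminases, myalgias and raised CPK as the commonest statin effects, so those removals would lean towards simvastatin. Lipid-rule removals would lean towards placebo. How often the lipid rule acts is unclear, because Table 3 shows no lipid panel at months 3 or 6.

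Cognition has a more specific problem. It is monitored because of concern about statin harm, and it is compared by the same ANCOVA of month-12 scores. A subject who declines mid-study and is removed has no month-12 score, so the safety rule takes affected subjects out of the safety comparison. At stake are how far the four CSF p-values can be read as a randomised comparison, and whether the between-arm cognitive test can show the harm it is there to detect.

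**Working it through.** **1. The plan's own figures.** From Sample Size, Effect Size, and Power: N = 120, about 17% dropout, alpha = 0.05/4 = 0.0125 (two-sided assumed), 80% power at 0.68 SD and 90% at 0.77 SD.

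- Completers per arm: 120 × 0.83 / 2 = 49.8, so about 50 of 60, with about 10 lost per arm. (The 10% dropout in the randomisation paragraph would give 54.)
- Power by non-central t with 50 per arm: 80.2% at 0.68 and 90.2% at 0.77. Both figures reproduce.

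**2. CSF bias under no true effect.** The documents give no link between dropout and the biomarkers, so every link below is an assumption.

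*Formula.* One arm loses a share p from the tail of a variable correlated r with the CSF residual; the other arm loses subjects at random. Bias = r × φ(z_p)/(1 − p). For p = 0.17: z = −0.954, φ = 0.253, and 0.253/0.83 = 0.305.

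| r | Bias (SD) | Type I error (nominal 1.25%) |
|---|---|---|
| 0.1 | 0.03 | 1.35% |
| 0.2 | 0.06 | 1.6% |
| 0.3 | 0.09 | 2.2% |
| 0.5 | 0.15 | 4.0% |
| 1.0 (bound) | 0.30 | 15.4% |

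*Simulated ANCOVA* (60 per arm, 20,000 trials per case, baseline to month-12 correlation 0.5 to 0.9, dropout correlated 0.3 or 0.5 with the month-12 value, bias in SD of change):

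- 10 lost per arm, same link in both arms: 0.00 SD, type I error 1.2 to 1.5%.
- 12 against 8 lost: 0.01 to 0.04 SD.
- Link in one arm only: 0.04 to 0.11 SD, type I error 1.3 to 3.4%.
- 3 of 60 lost per arm, close to the pilot's 1 of 24, link in one arm: at most 0.04 SD.
- One-arm link, but 5 of the 10 still giving month-12 CSF: 0.02 to 0.05 SD.

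**3. Cognition.** Assumptions: true mean harm 0.30 SD; 10 tests plus MoCA, inter-test correlation 0.3; retest correlation 0.5 to 0.9 (the protocol gives .51 to .70 for the RAVLT); one interim check; removal when MoCA and at least two tests each fall by 1 SD or more.

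| Pattern of harm | Completer estimate (SD) |
|---|---|
| Uniform | 0.30 |
| Persistent individual variation (SD 0.3 to 0.5) | 0.25 to 0.28 |
| All harm in 20% of subjects (0.30/0.20 = 1.5 SD each) | 0.05 to 0.12 |

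With the four scheduled MoCA checks, the last row falls to 0.01 to 0.03 SD. A separate four-check model (14 tests, reliability 0.6, 1 SD harm in 10%) gave completer estimates of 0.024 against a true 0.096 if harm stays in the same people, and 0.093 against 0.095 if it is transient. Persistence is therefore the deciding condition.

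**4. How far the existing secondary model helps.** In the 20% case, entering the trigger-visit score as a separate visit gives 0.06 to 0.16 SD, whereas using it as the follow-up score gives 0.29 to 0.31 SD. The unspecified choice matters. A month-12 battery on half of those removed gives 0.19 to 0.22 SD if harm persists off drug.

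**5. Power if all 10 stoppers per arm return** (60 per arm, 0.68 SD in those staying on drug):

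- No effect kept: 0.68 × 50/60 = 0.567, power 71%.
- No effect kept, and 3 placebo stoppers start a statin with full effect: 0.68 × (50 − 3)/60 = 0.533, power 65%.
- Half the effect kept: 0.68 × 55/60 = 0.623, power 81%.
- Undiluted: 0.68, power 88%.

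**The case against.** The best defence is that the plan already contains most of the remedy. It has an all-randomised mixed model, a completer against non-completer comparison, a missingness assessment, a full battery at the triggering visit, a discontinuation visit for outcome measures (probably including CSF, as the primary outcome) and DSMB data coded by arm. Loss may also be well below 17%: the protocol cites under 1% withdrawal for statin reactions in practice, and 23 of 24 pilot subjects completed. The trial is described as proof-of-concept. This stands, and it keeps the CSF part small.

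The cognitive illustration is also extreme. It needs a fifth of subjects to lose 1.5 SD on every test and on MoCA, and to stay there, while the protocol's literature review describes such events as very rare. In that case removals would themselves speak: with one check, 17 to 20% against 0 to 8% removed. For example, 10 against 0 of 60 gives Fisher p = 0.001, although 12 against 5 gives only p = 0.11. This also stands.

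The simulations are not calibrated to this protocol. One check is fewer than the four scheduled. Four-check runs at moderate retest correlation remove about 15% or more per arm with no drug effect at all, nearly the whole dropout allowance, whereas the protocol describes MoCA retest as high. The ranges show direction and conditions; they are not forecasts.

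What does not fall is the structural point. The mitigations are secondary, and outside psychiatric re-entry none supplies month-12 data on removed subjects.

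**Conclusion.** The point holds as a cheap improvement worth making; it is not a threat to the design. For CSF, bias of about 0.00 to 0.15 SD is possible under assumed links, its direction is unknown, and it is small against 0.68 SD. For cognition, the completer comparison would understate harm that persists in affected individuals and would not understate uniform harm.

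Three stronger readings are tempting and unsupported:

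- *The primary biomarker results would be materially biased.* Nothing in the documents links dropout to CSF. The 0.30 SD bound requires perfect selection in one arm and none in the other.
- *Cognitive harm would go unseen.* Removals and trigger-visit scores exist, and the DSMB sees data by arm. Only the planned between-arm test is weak.
- *Removal ends all follow-up.* A discontinuation visit, laboratory follow-up and psychiatric re-evaluation are provided. What is missing for most is the month-12 lumbar puncture and battery.

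**What to change.** 1. In Monitoring safety of participants, Criteria for termination from study and Protection Against Risk: meeting a removal rule stops study drug only. The already scheduled month-12 lumbar puncture and battery are still done if the subject is willing and it is safe (no puncture in pregnancy). Use one cognitive threshold throughout. This step brings most of the gain.
2. In Primary analysis plan: make an all-randomised, as-assigned mixed model of baseline and month-12 values primary, with the ANCOVA covariates and a stated missing-at-random assumption. Keep the completer ANCOVA as a sensitivity analysis. State openly that this alters the planned mixed model, because early-termination CSF moves to a sensitivity analysis. Without step 1 this changes little.
3. Report cognitive removals and trigger-visit battery scores by arm. Use trigger scores as the follow-up value in a safety sensitivity analysis, noting that they are selected for being low: under uniform 0.30 SD harm this gave 0.30 to 0.32 SD with one check and 0.32 to 0.34 SD with four.
4. Record lipid-lowering drugs started after removal and report a sensitivity analysis for them.

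Cost: wording changes and no lumbar puncture beyond the two scheduled, but people who have stopped drug are asked back for a 28 ml puncture and some will refuse. Including off-drug subjects estimates the effect as assigned, which may be diluted: the power cases in step 5 of the working run from about 65% to 88%, against 80% as planned. If 5 of 10 stoppers per arm return, power is 76% with no effect kept, 80% with half kept and 85% undiluted. Those who do not return still rest on the missing-at-random assumption.

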### **Expected results and interpretation**

Our hypothesis is that 1-year of treatment with simvastatin, a CNS permeable statin, will reduce CSF levels of t-tau, p-tau181, and p-tau181:t-tau ratio; and increase CSF level of BDNF in Veterans with blast concussion mTBI and PPCS compared to treatment with placebo. We speculate that simvastatin may produce neuroprotective benefits through effects on multiple biochemical pathways, including, but not limited to, reduction of tau phosphorylation, altered A $\beta$  production, increased production of brain neurotrophic factors, and reduction of brain antioxidant and anti-inflammatory effects. We expect to replicate our pilot study findings of reductions in CSF concentrations of t-tau, p-tau181 and increase in CSF BDNF associated with simvastatin treatment. If this finding is confirmed, we will further examine how t-tau, p-tau181, and p-tau181:t-tau ratio are related to changes in other CSF AD markers (i.e., changes in levels of CSF BDNF, A $\beta$ 4, IL-6, IL-8, S100 $\beta$ , and/or F2-isoprostanes) in an attempt to further understand the mechanisms by which statins act to reduce tau phosphorylation and/or A $\beta$ 42 turnover.

Based on our preliminary findings (*see Preliminary Studies*), we also expect a significant reduction in CSF A $\beta$ 42 after one year of treatment with simvastatin compared to placebo. However, a caveat is that reduction in CSF A $\beta$ 42 after statin treatment is difficult to interpret in a straightforward manner, as it could imply either reduction in brain A $\beta$ 42 production (which potentially could prevent formation of neuritic plaques) or potentially sequestration of CSF A $\beta$ 42 into neuritic plaques in the brain. However, cognitively normal persons in the proposed age range of 21-50 are extremely unlikely to exhibit changes CSF A $\beta$ 42 over the course of a year unless these changes are due to the treatment intervention. To aid in interpretation of CSF A $\beta$ 42 findings,

presence or absence of the APOE\*4 allele (which is associated with lower CSF A $\beta$ 42 in cognitively normal persons - likely reflecting incipient amyloid pathology) as well as pretreatment ratios of CSF t-tau/A $\beta$ 42 will be used as covariates during the analyses.

## PROTECTION OF HUMAN SUBJECTS

### (1) Risk to Subjects

(a) Human Subjects Involvement and Characteristics: Participants will be 120 Iraq and Afghanistan Veterans between the ages of 21 and 50 who are in good general health and who meet the specific study inclusion/exclusion criteria as described in detail in the "Research Design and Methods" section above. Persons of all races and ethnicities and both genders will be eligible. Participants will be naïve for statins, and will have either normal LDL cholesterol or mildly elevated LDL cholesterol which does not require drug therapy per NCEP/ATP-III guidelines.

Specific inclusion criteria include documented hazardous duty in Iraq and/or Afghanistan with the U.S. Armed Forces and exposure to blast concussion (with >6 months since last blast exposure) sufficient to meet ACRM criteria for mTBI (*described in detail above*). Participants will have a BMI between 18 and 36 (BMI outside this range may affect the biomarker measurements and increase difficulty of LP).

Exclusion criteria for all participants will include: penetrating head wound; seizure disorder; insulin-dependent diabetes; alcohol abuse or other substance abuse; DSM-IV diagnosis of schizophrenia or other psychotic disorder, bipolar disorder, or dementia; use of exclusionary medications (used in the 4 weeks prior to screening) or receiving any investigational medication; contraindication to LP (spinal deformity, severe lumbar spine disease or infection at LP site, bleeding tendency or on anticoagulant medication); platelet count less than 100,000 at time of LP.

Women of childbearing potential must have a negative pregnancy test at screen and must agree to use an acceptable form of birth control for the duration of the study. We suggest that women continue to use birth control for one full menstrual cycle after completing or withdrawing from the study.

It is likely that economically disadvantaged subjects will participate in this study. This may be considered a vulnerable population. While subjects will receive up to \$650 for completion of the study, it is not felt that degree of remuneration will represent any form of economic coercion to those that are economically disadvantaged, considering the potentially significant time commitment we are asking the subjects to make. Prisoners and institutionalized individuals will not be involved in this study.

(b) Sources of Materials: Research materials from living human subjects will be results from clinical/neuropsychiatric assessments; blood samples collected for screening labs, DNA, and biomarker analysis; and CSF collected for biomarker analysis. These procedures will be done specifically for research purposes. In addition, existing medical records will be reviewed to confirm eligibility for participation. Consent will be obtained before reviewing existing medical records.

(c) Potential Risks: Risk to subjects is modest. All risks are research risks, none are therapeutic risks. They include possible stress from undergoing clinical/neuropsychiatric assessment, risks of blood draw/i.v. placement, LP, risks of taking simvastatin, and potential loss of confidentiality.

*Risks of Simvastatin*: Simvastatin is used widely for lowering cholesterol and for primary prevention of cardiovascular and cerebrovascular disease at the doses proposed in this application. It is generally safe and well tolerated. The most common adverse effects in clinical use are elevated liver transaminases, myalgias, and elevated CPK. However, the literature suggests that the rate of adverse reactions necessitating withdrawal from statin therapy is less than one percent in clinical practice. Simvastatin is classified by the US FDA as Pregnancy Category X and is contraindicated in women who are pregnant or nursing. All female subjects of child bearing potential will have urine pregnancy tests at every study visit, will be required to be using a reliable form of contraception, and will be told of the risks of becoming pregnant while participating in this study. We also advise women of childbearing potential that they wait one full menstrual cycle after stopping the medications offered in this study before becoming pregnant.

Simvastatin is highly lipophilic and shows good ability to cross the BBB. Because brain cholesterol is synthesized *in situ* within the brain, the ability of a statin to penetrate the BBB may be important in proving neuroprotection. However, some concerns regarding potential adverse effect of brain penetrating statins have been raised in recent years because adequate brain cholesterol bio-availability is essential for the proper functioning and physical integrity of brain cells. It has been hypothesized that long-term reduction of cholesterol in the brain with statins that readily cross the BBB may adversely affect cognitive functioning. Two case reports of single individuals reporting memory impairment in association with simvastatin use have appeared in the literature. However, other reports indicate that these events are extremely rare. Wagstaff et al reviewed

over 11,000 adverse events reported to the Food and Drug Administration's MedWatch program between November, 1997, and February, 2002, for simvastatin and pravastatin and were able to identify only 37 case reports of cognitive adverse effects (e.g., short-term memory loss, amnesia, confusion), none of which was documented with formal cognitive testing.

Available prospective, randomized, double-blind, placebo-controlled trials have provided scant evidence of statin-induced cognitive impairment as assessed by formal neuropsychological testing. In a study of 209 hypercholesterolemic adult subjects treated with lovastatin 20 mg/d or placebo for six months, Muldoon et al. found that the statin-treated subjects showed slightly less improvement over time in comparison to placebo-treated subjects on tests of attention and psychomotor speed, but did not differ on tests of mental flexibility, working memory or memory retrieval. In a follow-up study comparing placebo, simvastatin 10 mg/d, and simvastatin 40 mg/d, the same pattern of lesser improvement in simvastatin vs. placebo-treated subjects was seen only on some tests of attention and psychomotor speed but not on others. However, four independent studies did not find any differences in performance on a broad range of neuropsychological tests between those treated with BBB crossing statins and those treated with non-BBB crossing statins. Finally, Gibellato et al. studied 136 middle-aged military aircrew personnel treated with placebo, pravastatin 40 mg/d, or simvastatin 40 mg/d for 28 days and found no effects on performance on a battery of computerized tests demonstrated to be sensitive to detecting subtle impairments in complex cognitive processes involved in piloting aircraft (the Federal Aviation Administration CogScreen Aeromedical Edition).

The prospective trials of statin effects on neuropsychological measures of cognition all had small sample sizes and may therefore have been underpowered to detect changes in cognitive function. However, secondary analyses of data from the Heart and Estrogen/progestin Replacement Study of 1037 postmenopausal women found that declines in MMSE scores over four years of follow up were less in statin users versus non-users. The larger Cardiovascular Health Study of 3,334 patients found a trend towards lesser declines in Modified Mini-Mental State Examination (3MS) scores in statin users versus non-users with hypercholesterolemia. Of note, the overwhelming majority of subjects in these studies were elderly at the time of enrollment and therefore at elevated risk of experiencing cognitive adverse effects of statins. That these elderly subjects did not demonstrate cognitive adverse effects of statins argues strongly for their safety in other vulnerable populations, such as Iraq and Afghanistan Veterans with repetitive mTBI.

The absence of short-term changes in cognitive function in these large N studies argues persuasively that the effect sizes of any potential adverse cognitive effects must be exceedingly small. As cogently stated in a recent review of statin safety, "These measurements in large numbers of participants in randomized trials establish beyond doubt that statins cause no perceptible decline in cognitive function". Consistent with this low rate of adverse events, simvastatin was approved for over-the-counter sale in the United Kingdom in 2004. In addition, a US Neurology Expert Panel charged with the task of reviewing the scientific evidence related to adverse effects of statins recently concluded that statins do not impair memory or cognitive function; however, this expert panel also recommended that "investigation of statins should include secondary outcome measures that address potential adverse events," we will monitor subjects in our study for changes in cognitive function by means of a brief global cognitive scale at the 6 week and 3- 6- 9- and 12-month visits.

**Risks of venipuncture:** Removal of blood by a needle and Vacutainer or syringe poses a small risk of pain or bruising at the site of the needle stick. Infrequently, subjects may experience fainting or dizziness and there is also a slight risk of infection at the site of the needle stick.

**Risks of Lumbar Puncture:** The risk of serious effects from LP (infection, nerve root damage) is extremely low. Rarely, patients may experience transient local pain either at the site of the puncture or in the distribution of the sciatic nerve if the nerve roots of the *cauda equina* are stimulated. Because the LP is performed well below the termination of the spinal cord and because the nerve roots readily move aside from the spinal needle, the possibility of permanent damage to a nerve root is very remote. Subjects with blood clotting abnormalities, on anticoagulant medications, or with inadequate platelet function will be excluded. A previously common (approximately 20% in young persons) adverse effect was post-LP headache. The incidence of headache is a function of the diameter and type of spinal needle used and not the amount of fluid removed. Prior to the past 8 years, our method of using a very fine 25g Quincke (cutting) spinal needle reduced the incidence of post-LP headache to less than 5%. Over the past 8 years, we have instituted use of the 24g Sprotte atraumatic spinal needle. The Sprotte needle has been recommended in recently published guidelines for reducing risk of post-LP headache. We have performed over 300 LPs since we began using the Sprotte spinal needle and in our hands, risk of post-LP headache is now less than 1%, similar to that reported in the literature for the 24g Sprotte needle.

In addition, it should be noted that removal of up to 30 cc of CSF does not increase the incidence of headache since CSF is rapidly produced. CSF is produced normally at the rate of 0.35cc/5 minutes; it is estimated that the amount of CSF that we will draw will be replaced in about 6-7 hours. The post-LP headache is thought to occur due to a persistent leak of CSF from the hole left in the dura by the larger bore Quincke spinal needle used in commercial LP kits which routinely contain an 18 or 20 g Quincke spinal needle, rather than the amount of CSF removed acutely. This leads to a depletion of the normal CSF hydraulic “cushion” and leads to a headache the day after the procedure. We reduce the risk of CSF leak by having the subject lie in bed for one hour after the procedure, having them increase their fluid intake, and by instructing subjects not to engage in any strenuous activity for the 24 hours following the procedure. All investigators performing LPs are very experienced in performing this procedure in these subject populations.

Headaches following LP, if they occur, are usually mild to moderate and may last for 24-48 hours; such headaches are successfully managed with acetaminophen and caffeine (in the form of a soft drink, Mountain Dew). In unusual cases, typical post-LP headache, which is posturally sensitive, may occur; these may be fairly severe and can last as long as a week with conservative management. Our approach to treatment of severe typical post LP headache is the epidural blood patch, performed on the first morning of severe post-LP headache (usually the day following LP). Epidural blood patch consists of the injection of 30 cc's of the subject's own blood into the epidural space over the lumbar puncture site. This procedure is done by an anesthesiologist and usually provides immediate relief of post-LP headache. The Anesthesiology Service at VA Puget Sound Health Care System has agreed to perform these procedures if necessary and has quite graciously and successfully performed them in the past.

We measured stress hormone responses to LP in subjects with AD and young and older normal subjects. Stress hormone responses (cortisol, norepinephrine and epinephrine) in plasma and CSF were reduced in AD subjects compared to young or older normal controls. These stress hormone responses were consistent with the lack of behavioral arousal observed in the AD patients in response to LP. More recently, we have analyzed data from 428 research LPs performed on 342 subjects (67 with AD or MCI, and 275 cognitively normal adults). The frequency of any adverse event (11.7%), clinically significant adverse events (3.97%), and typical post-lumbar puncture headache (PLPHA) (0.93%) was low. Risk of PLPHA was unrelated to age, gender, position during LP, mls CSF collected, or minutes of recumbent rest following LP.

*Risks of Genetic Studies:* We will be testing for APOE genotype. The APOE-ε4 allele has been implicated as a risk factor for development of AD in later life. However, APOE type should not be considered a genetic test for AD since the results will not conclusively determine whether a person or any of his/her relatives have or might develop AD. Subjects are informed that results of APOE testing will be used for research purposes only and that subjects will not be informed of their APOE genotype. Subjects will be told that if they wish to know their APOE genotype, that they can have the testing done at a commercial lab at their own expense.

The Genetic Nondiscrimination Act of 2008 protects subjects against risks to employability and access to health insurance due to participation in genetic studies. However, it is theoretically possible that participation in genetics studies may jeopardize access to life insurance, disability insurance, or long-term care insurance if involvement and/or results of the study become part of the medical record. Procedures to minimize such risk are described below.

*Risks of Clinical Assessment and Neuropsychological Testing:* Risks due to clinical assessment procedures are modest. Subjects may experience stress similar to that of a standard clinical evaluation for memory complaints or dementia. Subjects may also receive information that they are cognitively impaired. Such information may be distressing to a subject. The neuropsychological assessment battery may cause fatigue and/or unpleasant affective states due to the large number of individual tests. Some of the clinician and self-administered assessment instruments may cause participants to focus their attention on traumatic combat-related experiences and as a result may produce transient subjective distress. However, these combat experiences are routinely assessed and discussed as part of standard clinical care.

*Risks to Confidentiality:* There is a risk of loss of confidentiality. Procedures to address protection against loss of confidentiality are addressed below.

